10.0 Study Design / Methods

ARMS 1, 2, and 3: Once a participant has consented and been enrolled they will be randomized by computer (stratified by gender) to one of three treatment groups and the PI and/or their designee will set up a home visit appointment to meet with the participant to obtain baseline data (Table 1). Part of the baseline screening includes the PROMIS Emotional Distress-Depression Short Form 8a. If a participant scores in the severe depression category (raw score 33 and above) a referral will be placed to a mental health professional. Additionally, participants that score in the moderate depression category (raw score 23 to 32) further screening for suicidal ideation will take place. If the participant would admit to suicidal ideation at any time during the study, an emergent mental health consult will be placed through the Charleston/Dorchester Mental Health Center Assessment/Mobile Crisis.

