The participant will then be trained on the use of the tablet including the application that will record and transmit their self-entered pain and fatigue symptom scores, the vital sign measuring equipment as well as the video platform for the nurse and self-management program to which they are randomly assigned. The vital sign recording equipment have all been FDA approved and gone through multiple rounds of formal verification. These are also Medical University of South Carolina (MUSC) and South Carolina (SC) Telehealth recommended devices as MUSC is arm of SC Telehealth Alliance. The tablet will be an iPad air 2, which has the communication protocol to connect to all these devices and send encrypted data securely back to servers. In addition, the participants will be given and receive training on a Garmin Vivofit wearable activity tracker that is able to record, steps taken per day, heart rate, distance walked, stairs climbed, and sleep. Garmin Vivofit wearable fitness trackers meet high reliability and validity requirements for parameters such as step counts (Simunek et al., 2016). The training will be conducted via a prerecorded video shown to participants on their tablet at the initial meeting that also explains the program rationale, use of the tablet, activity tracker, and video and app platforms. This video will allow participants access to training at all times in case of issues or questions surrounding the equipment. The PI will contact the participant via their tablet on a weekly basis via the HIPAA compliant telehealth platform Vidyo. Vidyo, a real-time software video communication tool, is HIPAA Compliant with all of the media, signaling, and user login being encrypted to ensure patient privacy and compliance (Vidyo, 2014).²⁸ Each tablet will contain the app "Activate for Life". This app will allow the participant to transmit, via Bluetooth technology their blood pressure and pulse. The app also allows the participant to rate their pain and fatigue scores on a 1-10 scale, document their daily activity and their use of pain medication, and has the ability for the participants to record a voice diary of their daily progress or thoughts. Each participant will receive a blood pressure cuff and will take their blood pressure prior to participating in their PA for the day. The blood pressure and pulse information from the blood pressure monitor will be transferred via Bluetooth to the Activate For Life app on the participants iPad. Once the app has received the data, it will automatically upload the information to the server at MUSC and will be available to be reviewed by the research team. The app will also allow for the participants to input their pain and fatigue scores which will be utilized to monitor pain scores on a daily basis. The vital signs and pain scores will allow for individualizing of the physical activity program to increase or decrease activity based on worsening, improving, or stability of participant's pain as measured by the pain score or through prolonged elevations in blood pressure or pulse. Weekly telehealth visits will allow for delivery of each conditions intervention components, review of pain and/or fatigue, VS, and sleep data. These data will be assessed by the PI and discussed during the weekly telehealth visits with the participants. The burden of self-monitoring and data entry will be captured during feasibility assessments. Saliva samples will be collected from all groups at the beginning and end of the sessions on week 1 and 12 to measure salivary biomarkers including cortisol, and 1,5-AG. Feasibility

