This condition will incorporate OEP and GYYB as above and will also include behavioral activation to address motivation and affect. Behavioral Activation incorporates daily planners and worksheets to identify and rate reinforcing behaviors and is often used in conjunction with other interventions because components of these interventions are easily incorporated into the daily planner based activities. Each participant outlines general values and specific behaviors that 'demonstrate' each value, compiling a list of the latter. This list is then used to generate 10 to 20 highly defined values-based, reinforcing activities. Next, this list is combined with the activities outlines in Otago and GYYB and this master list is used to schedule these values-based activities for the next two days. One of the strengths of the BA protocol, relative to other cognitive behavioral and activation-based interventions, is that it is designed for implementation over a brief period. Additionally, sessions of the often require as few as 15-30 minutes of contact time due to the straightforward, simple structure of these sessions. Patients begin with a weekly self-monitoring exercise, charting behaviors and mood every hour, that serves as a baseline assessment of daily activities, and orients the patient to the quality and quantity of his or her activities on a daily basis. Also, baseline assessment assists in generating ideas about activities to target during treatment.

Session 1: Begins with rationales for Behavioral Activation. The core points made are that what one does often plays a role in how one feels. Clients then proceed to identify 5 classes of values (e.g., family, work, spirituality) with specific behaviors that 'show' the patient's value, thus the treatment is tailored for each individual. For example, the value 'time with family' might be shown by 'throwing the baseball with son for 20 minutes'. Lists of specific behaviors are derived for each value and written on the daily planner. Participants are then given a daily planning calendar and behaviors that are reinforcing and relatively easily accomplished are planned each day, for two days in advance with the objective of planning at least 2 hours of reinforcing activities and scheduled homework from Otago and GYYB each day. Session 2: Begins with a review of homework and verbal reinforcement of completed planners, completed reinforcing behaviors, completed Otago and GYYB homework,

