restatement of the rationale (ie., that what one does affects how one feels and doing positive things will help one to feel positively), and problem solving. Behaviors that were consistently planned but not completed are removed and alternative behaviors suggested. The next 2 days' activities are planned. This session usually involves a significant amount of problem solving, and identification of avoidance, with planning in place to counter this avoidance. Sessions 3-4: These sessions begin with a review of homework, followed by asking the patient to state, in their own words, their interpretation of the rationale for Behavioral Activation. Obstacles to completing behaviors are discussed and additional exposure-based and reinforcing behaviors are generated. The next 2 day's activities are planned. Session 5: Includes discussion of the rationale and treatment gains obtained thus far. Discussion is also centered on the need to continue planning activities and using a daily planner for at least 6 months. Relapse prevention strategies are reviewed. Additional sessions are conducted every other week until week 12 (Otago and GYYB completion).

Table 2: Measurements/Instruments/Interventions and Time Points		
Major tasks and domains; monitor/ evaluate	Measures/instruments/questions and Cronbach's alpha ()	Data sources and time points
Screening	Ability to ambulate 150 feet with or without assistive device; Short version of Test for Functional Health Literacy in Adults (0.97) ³⁷ Tablet Computer Familiarity Questionnaire (0.92) ³⁸ Mini-Cog ²⁶	Participant interview and observation; Baseline
Demographics	Personal health, medical, health history—co-morbidities, medications, use of pain medications, race/ethnicity	Participant interview; Baseline
Weekly nursing self-management	Review weekly diary entries, pain scores, yoga and /or Otago progress, fatigue, and sleep.	Weekly
Reach: Sample Recruitment	Progress monitoring of sample representativeness; types of recruitment activities and rates; % eligible, consented, oriented	Tracking forms; weekly quality checks by PI; weekly team meetings
Effectiveness: Functional impacts Pain	Numerical rating scale NRS (0.99) ³⁹ PROMIS Pain Interference Short Form 6b (0.98) ⁴⁰ PROMIS Pain Behavior Short Form 7a (0.98) ⁴⁰ PROMIS Fatigue Short Form 6a (0.91) ⁴¹	Baseline; Daily; Study end Baseline; Study end Baseline; Study end Baseline; Daily; Study end

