15.0 Risks to Subjects

The risks associated with this intervention are not considered greater than those that patients would otherwise be exposed to when engaged in an routine physical activity exercise program. Overall, potential risks associated with participation in the study are viewed to be minimal. However, as with all studies, there are inherent risks involved with the conduct of human subject research that gathers Protected Health Information (PHI). Participants will be made aware of these risks during the Informed Consent process. Identified study risks include: Physical discomfort, emotional distress, social wellbeing, Loss of privacy, and randomization.

Physical discomfort. Participants with pre-existing medical conditions that would make increase in physical activity dangerous to their health will be excluded from the study. There may be minor physical discomfort from the increase in physical activity; however, the potential risk to all subjects is minimal. The participants' pain and fatigue scores will be assessed on a weekly basis by the PI, who is a Board-Certified Family Nurse Practitioner, which will allow for further determination of any untoward effects of participation in the physical activity program. The PI will be communicating with the participants via telehealth visits on a weekly basis to allow for further follow-up of any physical issues with the program.

Emotional distress. Participants will be asked to provide information about their self-reported pain and fatigue, social isolation, depression and demographic data. These questions pose an anticipated low psychological risk, e.g. for anxiety, if participants appear upset by questions about their health issues, they will be instructed that if they do not wish to answer a question, they can skip it and go to the next question.

Social well-being. There is low potential for adverse social effects in this research study. Through bi-weekly telehealth visits with nurses, participants will have social support during their participation.

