Loss of privacy. PHI from participants will be gathered and stored electronically on secure and encrypted servers and there are risks associated for the loss of privacy and confidentiality. As well as having a comprehensive DSMP that details data safety, handling, monitoring, storage and security procedures, we will further minimize the potential for loss of confidentiality through the physical separation of participant names from their research record.

All participants will be screened for depression using the PROMIS Emotional Distress-Depression Short Form 8a. If a participant scores in the severe depression category (raw score 33 and above) a referral will be placed to a mental health professional which could result in loss of confidentiality. Additionally, participants that score in the moderate depression category (raw score 23 to 32) further screening for suicidal ideation will take place. If the participant would admit to suicidal ideation at any time during the study, an emergent mental health consult will be placed which could also lead to loss of confidentiality.

Randomization. Participants are being assigned to one of three study groups and treatment programs by chance. Each exercise program may prove to be less or more effective or have more or less or unknown side effects than the other or other available treatments. Participation in the study is completely voluntary and participants may withdraw their consent at any time.

If participants should experience any symptoms during physical activity and medical attention is needed, resource numbers of local healthcare providers and hospital system emergency services are provided to all subjects to access in the same manner they would with any emergency that they encountered. The PI is a board-certified Family Nurse Practitioner and will be available as a resource by telephone during regular business hours. This information (contact resources) is provided in writing to all subjects who choose to consent and enroll in the study.

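### The suicidal-ideation screen is tied to moderate depression scores (23 to 32), so participants scoring severe (33 and above) have no required screen

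*Protocol*

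**What the plan says.** Section 10.0 (Arms 1, 2 and 3) makes the PROMIS Depression Short Form 8a part of baseline screening and sets three rules:

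- **Severe band:** "If a participant scores in the severe depression category (raw score 33 and above) a referral will be placed to a mental health professional".
- **Moderate band:** "Additionally, participants that score in the moderate depression category (raw score 23 to 32) further screening for suicidal ideation will take place".
- **Disclosed ideation:** "If the participant would admit to suicidal ideation at any time during the study, an emergent mental health consult will be placed". The consult goes through a named mobile crisis service.

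Section 15.0, under loss of privacy, gives the same three rules. The moderate-band wording there is "participants that score in the moderate depression category (raw score 23 to 32) further screening for suicidal ideation will take place".

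Other contacts are described as follows. In Section 10.0: "Weekly telehealth visits will allow for delivery of each conditions intervention components, review of pain and/or fatigue, VS, and sleep data". In Table 2, the weekly nursing entry: "Review weekly diary entries, pain scores, yoga and /or Otago progress, fatigue, and sleep". In Section 15.0, under physical discomfort, the investigator's telehealth contact is "on a weekly basis to allow for further follow-up of any physical issues with the program". Mood charting appears in the Behavioral Activation condition: "Patients begin with a weekly self-monitoring exercise, charting behaviors and mood every hour".

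**The concern.** An ideation screen triggered by a depression score would normally apply from a threshold upwards. Here it applies inside a closed range and stops where severity is greatest. Staff who follow the written rule must ask the moderate scorers and are not told to ask the severe ones.

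At stake is whether ideation in the highest-scoring participants is picked up at the visit where the score is obtained. The protocol treats admitted ideation as an emergency but sets no time limit on the referral that severe scorers receive. A severe scorer with ideation who does not volunteer it could therefore wait for an appointment of unspecified date, when one question at the visit would have triggered the emergent route.

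**Working it through.** **The rules side by side.** The protocol gives no figure to reproduce, so the check is a comparison of the text. Sections 10.0 and 15.0 agree on every row.

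| Raw score | Ideation screen required | Referral required | Emergent consult |
|---|---|---|---|
| Below 23 | No | No | If ideation is admitted |
| 23 to 32 | Yes | No | If ideation is admitted |
| 33 and above | No | Yes | If ideation is admitted |

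A one-point rise from 32 to 33 adds the referral and removes the required screen.

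**Does anything else require the question for severe scorers?**

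- *Emergent consult.* It covers any score at any time, but it starts from the participant's admission. For the severe band no step obliges anyone to ask.
- *Weekly contacts.* The listed content is intervention delivery, diary entries, pain, fatigue, vital signs, exercise or yoga progress, sleep and physical issues. No mood or ideation question is listed.
- *Mood charting.* It is described only for the Behavioral Activation arm, which is 10 of 30 participants. The other 30 − 10 = 20 have none described.
- *Eligibility (Section 5.0).* The psychiatric-disability exclusion is put into practice through a Mini-Cog score, which is a cognitive test. Severe scorers can enrol, and Section 10.0 expects some to.
- *Safety monitoring plan for Arms 1 to 3 (Section 13.0).* It relies on participants reporting events and contains no ideation screen.
- *SAP.* It is silent on the point.

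**How many participants could be affected.** The documents give no distribution of depression scores. Sections 1.0 and 2.0 say only that anxiety and depression were high in the pilot. I therefore assume a severe share p of 2% to 20%. With n participants:

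- expected number severe = n × p
- chance of at least one = 1 − (1 − p)^n

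For n = 30 (Section 6.0, Arms 1 to 3):

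| Assumed p | Expected severe | Chance of at least one |
|---|---|---|
| 2% | 30 × 0.02 = 0.6 | 1 − 0.98^30 = 0.4545 (45%) |
| 5% | 30 × 0.05 = 1.5 | 1 − 0.95^30 = 0.7854 (79%) |
| 10% | 30 × 0.10 = 3.0 | 1 − 0.90^30 = 0.9576 (96%) |
| 20% | 30 × 0.20 = 6.0 | 1 − 0.80^30 = 0.9988 (99.9%) |

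In the 20 participants without Behavioral Activation the expected number is 20 × 0.02 = 0.4 to 20 × 0.20 = 4. If the Section 15.0 statement that all participants are screened for depression also covers Arm 4 (50 people in total), it is 50 × 0.02 = 1 to 50 × 0.20 = 10.

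These are counts of severe scorers. How many would report ideation if asked cannot be estimated from the documents.

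**The case against.** The best defence is that this is a stepped rule. Moderate scorers get no automatic referral, so staff must screen them to decide who needs escalation. Severe scorers skip that triage and go straight to a professional, who will probably assess risk. The referral is indeed a real safeguard. But the protocol neither dates it nor requires the professional to assess ideation, so it does not replace a question at the visit.

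A second defence is that the word *Additionally* signals a cumulative screen. That may have been the intent. The sentence nevertheless names the moderate category and its range, and does so in both sections. If the screen was meant to be cumulative, the correction merely records it.

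Third, there are further contacts: bi-weekly nurse visits for social support (Section 15.0), a voice diary in the app (Section 10.0), and reminders to report clinical deterioration (Section 13.0, Arms 1 to 3 plan, Section C). The investigator is also a nurse practitioner and may well ask anyway. All of these could bring distress to light, but none contains a required ideation question, and Section 10.0 allows a designee to handle the baseline visit.

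Some points against the size of the problem stand. The severe share is assumed, and the probabilities concern severe scores rather than missed ideation. The extension to Arm 4 is doubtful, because Section 10.0 places the rule under Arms 1 to 3, Section 15.0 speaks of three study groups, and Arm 4 has its own plan that elicits adverse events at every contact. Operating detail may also sit in the human-participants section or consent form to which the monitoring plan refers; neither was available.

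**Conclusion.** The concern holds. As written, the ideation screen is required at 23 to 32 and not at 33 and above, in both places where the rule appears, and nothing else in the available text fills the gap. That part rests on the wording alone.

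The number of people affected is conditional: 0.6 to 6 of 30 under the assumed 2% to 20% severe share. I put no weight on the Arm 4 extension.

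This is a participant-safety matter and changes no estimate, test or confidence interval. The sponsor should correct it. The SAP describes the analysis in the past tense, so the benefit to participants already assessed may be limited. Section 1.0 presents the pilot as groundwork for a full-scale randomised trial, which could inherit the rule.

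**What to change.** In Sections 10.0 and 15.0, replace the closed-range sentence and the severe-band referral sentence with:

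> Participants with a raw score of 23 or above will be screened for suicidal ideation at the same visit. Those with a raw score of 33 or above will also be referred to a mental health professional.

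Leave the emergent-consult sentence as it is.

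The cost is one wording change in two places, and in the consent form if it repeats the rule. The extra work is one ideation screen per severe scorer, 0.6 to 6 screens among 30 under the assumed range. Some screens may lead to an emergent consult, with the confidentiality risk that Section 15.0 already describes. Nothing changes for anyone scoring below 23.

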11.0 Specimen Collection and Banking

Saliva Sample Collection (all ARMS): One 3mL saliva samples will be collected from participants at each of the three study visits. At the first two visits (baseline and week 12) the samples will be collected before and after the 30 minutes GYYB session. Saliva will be naturally allowed to accumulate in the oral cavity and the participant will discharge it into the specimen tube (5 mL capacity) with lid. Due to COVID-19 precautions, participants will be given the option to either 1) drop off their saliva samples at MUSC CON, or 2) to arrange to have their saliva sample picked up from their place of residence or at a location that is convenient to both themselves and the researchers. Immediately after collection the saliva samples will be labelled with the participant's study ID number and the collection dates, and then placed on ice for immediate transportation to MUSC in a biohazard cooler. The samples will subsequently be stored at -80 degree C until analysis by [name] at his lab. For analysis, the samples will be slowly thawed, centrifugation at 14000 RPM at 4 degree C.

Salivary Biomarker Measurement (all ARMS): Owing to their possible involvement in pain and/or fatigue, the following biomarkers will be assessed in saliva: cortisol and 1,5-AG. [name] (Co-I) will perform the analysis of salivary biomarker expression in the saliva samples similar to their laboratory's recent reports (<https://www.ncbi.nlm.nih.gov/pubmed/27538513>; <https://www.ncbi.nlm.nih.gov/pubmed/25873979>; <https://www.ncbi.nlm.nih.gov/pubmed/25101659>). [name] has over 20 years of experience in ELISA and other biochemical techniques for biomarker measurement ([name], & Kuppuswamy, 2003; [name] et al., 2006; [name], Mani, Kasiganesan, Baicu, & Kuppuswamy, 2010; [name] et al., 2012; Moschella et al., 2013; Prabhasankar, Ragupathi, Sundaravavidel, Annapoorani, & Damodaran, 1993).

Specimen access and disposal (all ARMS): A chain of custody log will be maintained for the collection, handling and disposition of all participant biological specimens. [name] will only have access to unidentifiable biological data, which will be stored on MUSC secure servers. No genetic analysis or specimen banking will be conducted. Data will not be sent outside of the MUSC enterprise, and all specimens will be destroyed six months after study completion. As specified in the

Informed Consent document, participant's may withdraw their consent to participant in the study at any time. Revocation of consent either verbally or in writing will immediately withdraw the consent of the participant's specimen analysis for any collected and unanalyzed saliva samples to date. The PI will work directly with [name] to notify him of consent withdrawals and to unblind group allocations for analysis purposes.

